In case of lorbrena delay (≤ 2 days), bosentan could be administered twice daily during a maximum of seven consecutive days before lorbrena infusion, and supplied at the study center once daily on Day 1 (before lorbrena infusion).

All patients will receive a maximum of three cycles: two consecutive cycles of lorbrena, one cycle with and one cycle without bosentan co-administration (in different order depending on the study Sequence 1 or Sequence 2 of treatment), followed by a third cycle with lorbrena alone (this last optional for patients with clinical benefit). Patients will be randomized in a 1:1 ratio ([Figure 2](#)) to Sequence 1 (TR: Test- Reference; lorbrena + bosentan in Cycle 1) or Sequence 2 (RT: Reference-Test; lorbrena + bosentan in Cycle 2). Lorbrena will be administered as a 1-hour (-5/+20 min) intravenous (i.v.) infusion every three weeks (q3wk) via a central or peripheral vein. The dose of lorbrena will be 3.2 mg/m² for all patients when administered with and without bosentan. If toxicity occurs, the appropriate intra-patient dose level (DL) reductions will be implemented in the subsequent cycle. This DL reduction will be according to [Table 8](#).

Figure 2. Study design.

BOS, bosentan; LRB, lorbrena; TR, test-reference; R; randomized; RT, reference-test.

The enrollment of the patients will be simultaneous. However, if once the first three patients enrolled have completed Cycle 1 and Cycle 2, total lorbrena exposure does not allow an adequate PK assessment and if no unacceptable or life-threatening toxicities have occurred, the dose of lorbrena to be co-administered with bosentan in the remaining five patients can be adjusted accordingly.

This decision will be made by the Sponsor and the study Investigators. Therefore, the planned dose of lorbrena, when given with bosentan for the remaining five patients, will be based on the acceptability of the PK and safety results from the first three patients. If the initial three patients do not experience adverse events (AEs) which might require a dose-reduction, the dose of lorbrena may still be adjusted (based on the assumption of dose-proportional pharmacokinetics) to produce plasma lorbrena area under the curve (AUC) values that are comparable to those when lorbrena is given in the absence of bosentan. However, if toxicity occurs in the initial three patients, the appropriate dose-reduction of lorbrena will be implemented in the remaining five patients accordingly.

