3.4.2 Safety Profile

Treatment safety, including AEs, serious adverse events (SAEs) and laboratory abnormalities will be graded according to the NCI-CTCAE v.5. Additionally, treatment compliance, in particular dose reductions requirements and/or treatment delays due to AEs, and reasons for treatment discontinuation will also be described. Patients will be evaluable for safety if they have received at least one partial or complete infusion of lorbinecetin.

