7.4 Treatment Administration

Exposure to treatment will be described by treatment group.

Total cumulative dose, time on treatment, dose intensity and relative dose intensity, administration delay and dose reductions/omissions will be described following standard tables (detailed in Section 11, Appendix II). The reported cycle information on the case report form (CRF) pages will be used for the analysis.

Time on treatment, expressed in weeks, is defined as the last administration date of lurbinecetin minus the first administration date plus 31 days, except if the patient dies or starts a new antitumor therapy within 31 days from the last administration date, in which case the time on treatment will be the date of death or the start date of the new antitumor therapy minus the date of the first administration of the study treatment.

Total cumulative dose by drug, expressed in mg for both lurbinecetin and bosentan, is the sum of all the product doses received during the study, including the dose received in the last cycle.

For lurbinecetin, intended dose intensity is the planned dose per cycle divided by the planned number of weeks by cycle.

Absolute dose intensity is the actual cumulative dose divided by the number of weeks of treatment. As a convention, for this calculation, the duration of the last cycle will be the predefined cycle length (e.g. 21 days). Relative dose intensity (%) is the ratio of absolute dose intensity divided by the intended dose intensity.

The items « Infusion delayed: yes/no» and « Dose reduced: yes/no» present on the treatment exposure CRF pages will be used to calculate delays and dose reductions, respectively. For cycles considered as delayed by the Investigator, the length of the delay will be calculated as:

Duration of cycle delay: Date of the current drug administration – Date of the previous drug administration – the predefined cycle length (i.e., 21 days).

If the number of delays or dose reductions are very low, tables will not be presented and only listings will be shown.

7.5 *Subsequent Therapies*

A listing of subsequent therapies received after treatment discontinuation will be shown by total and treatment sequence group.

7.6 *Subgroup Analyses*

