11.1.2 Cycle Delays

Table 11.1.2.1 Summary of lurbinectedin dose delays

	S1 (TR)		S2 (RT)		Total	
	N	%	N	%	N	%
No. of patients treated						
No. of patients susceptible to have dose delay †						
No. of patients with any dose delay						
Drug related‡ AE						
Non-drug related AE						
Other reason						
No. of cycles administered						
No. of cycles susceptible to have dose delay ††						
No. of cycles with any dose delay ‡‡						
Drug related‡ AE						
Non-drug related AE						
Other reason						

† Excluding patients who received only the first cycle.

‡ Related or unknown relationship

†† All cycles excluding first cycle

‡‡ Denominator = Number of cycles susceptible to have dose delay

S1, Sequence 1; S2, Sequence 2; TR, test-reference; RT, reference-test.

Table 11.1.2.2 Length of dosing delay

	S1 (TR)		S2 (RT)		Total	
	N	%	N	%	N	%
Length of delay‡‡						
≤ 7 days						
> 7 to ≤ 14 days						
> 14 days						

‡‡ Denominator = Number of cycles susceptible to have dose delay

S1, Sequence 1; S2, Sequence 2; TR, test-reference; RT, reference-test.

Listing 11.1.2.3 Dose delays

Sequence	Subject	Cycle	Delay (days)	Reason for delay

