11.2.1 Display of Adverse Events

Table 11.2.1.1 Summary of adverse events

	BOS+LRB		LRB alone	
	N	%	N	%
No. of patients with any AE				
No. of patients with any treatment-related [†] AE				
Patients with any grade ≥ 3 AE				
Patients with any grade ≥ 4 AE				
No. of patients with any grade ≥ 3 treatment-related [†] AE				
No. of patients with any grade ≥ 4 treatment-related [†] AE				
No. of patients with any SAE				
No. of patients with any treatment-related [†] SAE				
No. of patients with any grade ≥ 3 SAE				
No. of patients with any grade ≥ 4 SAE				
Any grade ≥ 3 treatment-related [†] SAE				
Any grade ≥ 4 treatment-related [†] SAE				
No. of patients with deaths associated with AEs				
No. of patients with deaths associated with treatment-related [†] AEs				
No. of patients with dose delays associated with AEs				
No. of patients with dose delays associated with treatment-related [†] AEs				
No. of patients with dose reductions associated with AEs				
No. of patients with dose reductions associated with treatment-related [†] AEs				
No. of patients with AEs leading to treatment discontinuation				
No. of patients with treatment-related [†] AEs leading to treatment discontinuation				

[†] Related to combination, lirbinezdin or bosentan, or with unknown relationship

Number of patients with at least one event, treatment modification, withdrawal or death during the treatment with BOS+LRB or LRB alone.

BOS, bosentan; LRB, lirbinezdin.

Table 11.2.1.2 Treatment Related[†] (or with unknown relationship) Adverse Events. Worst grade per treatment

SOC/PT	BOS+LRB						LRB alone					
	All grades		Gr ≥ 3		Gr ≥ 4		All grades		Gr ≥ 3		Gr ≥ 4	
	N	%	N	%	N	%	N	%	N	%	N	%
...												

Notes: Percentage is based on number of patients by treatment, when applicable.

[†] Related to both or lorbinectedin or bosentan or with unknown relationship

BOS, bosentan; LRB, lorbinectedin.

Table 11.2.1.3 Lorbinectedin related[†] Adverse Events. Worst grade per treatment

SOC/PT	BOS+LRB						LRB alone					
	All grades		Gr ≥ 3		Gr ≥ 4		All grades		Gr ≥ 3		Gr ≥ 4	
	N	%	N	%	N	%	N	%	N	%	N	%
...												

Notes: Percentage is based on number of patients by treatment, when applicable.

[†] Related to lorbinectedin or with unknown relationship

BOS, bosentan; LRB, lorbinectedin.

Table 11.2.1.4 Bosentan related Adverse Events. Worst grade per treatment

SOC/PT	BOS+LRB					
	All grades		Gr ≥ 3		Gr ≥ 4	
	N	%	N	%	N	%
...						

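### The four dose-delay and dose-reduction rows of SAP Table 11.2.1.1, on their natural reading, count a modification under the cycle in which it is applied, not the cycle that caused it

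*SAP*

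**What the plan says.** Table 11.2.1.1 (SAP 11.2.1) summarises adverse events in two columns, BOS+LRB and LRB alone. Four of its 20 rows concern dose modification: delays and reductions, each for all AEs (for example "No. of patients with dose delays associated with AEs") and for treatment-related AEs. The only rule for placing a patient in a column is the footnote: "Number of patients with at least one event, treatment modification, withdrawal or death during the treatment with BOS+LRB or LRB alone".

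The derivation of delays and reductions is in SAP 7.4. It states: "The reported cycle information on the case report form (CRF) pages will be used for the analysis". The yes/no items for a delayed infusion and a reduced dose "present on the treatment exposure CRF pages will be used to calculate delays and dose reductions, respectively". It continues: "For cycles considered as delayed by the Investigator, the length of the delay will be calculated as" the current administration date minus the previous administration date minus 21 days. Tables 11.1.2.1 and 11.1.3.1 define the cycles open to a delay or reduction as "All cycles excluding first cycle".

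Protocol 3.1 says when a reduction takes effect: "If toxicity occurs, the appropriate intra-patient dose level (DL) reductions will be implemented in the subsequent cycle". Protocol 7.4 makes the start of a new cycle depend on recovery from the one before. In Sequence 1 (TR) this is checked on Day 1 of the new cycle. In Sequence 2 (RT) it is checked on Day 15 of Cycle 1, before bosentan starts, and again on Day 1 of Cycle 2.

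Protocol 3.4.2 makes these items part of the safety endpoint: "dose reductions requirements and/or treatment delays due to AEs, and reasons for treatment discontinuation will also be described".

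**The concern.** In this crossover, Cycle 2 is always on the other treatment from Cycle 1. A modification driven by Cycle 1 toxicity but recorded on the Cycle 2 exposure page belongs, by cause, to the opposite column from the one in which it would be counted.

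One secondary objective is the effect of bosentan on the safety of lurbinectedin, and Table 11.2.1.1 is where delays and reductions are set out by treatment. If a patient's column is decided by the modified cycle, the table does not describe what followed each treatment. It may suggest a difference where none exists, hide one, or point the wrong way.

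Modifications are plausible here. Grade 4 neutropenia is a reduction trigger (Protocol 7.5), and Protocol 1.1.3.1 reports it in 40% of patients in Cycle 1 at the first-in-human recommended dose. That dose was higher than the one used here, and the same section says neutropenia rarely caused delays.

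**Working it through.** The plan gives no figure for this point, so there is none to reproduce. The check maps each modified cycle to its cause and then works out expected counts.

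**Step 1. Which cycles can carry a modification.** The delay formula needs a previous administration, and the exposure tables exclude Cycle 1. That leaves Cycles 2 and 3.

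**Step 2. Treatment applied against treatment preceding** (sequences from Protocol 3.1):

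| Modified cycle | Treatment in that cycle | Treatment in the cycle before | Same? |
|---|---|---|---|
| TR Cycle 2 | LRB alone | BOS+LRB | no |
| RT Cycle 2 | BOS+LRB | LRB alone | no |
| TR Cycle 3 (optional) | LRB alone | LRB alone | yes |
| RT Cycle 3 (optional) | LRB alone | BOS+LRB | no |

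Three of the four slots differ. Only RT Cycle 2 can feed the BOS+LRB column, so with eight patients that column is capped at 4, while LRB alone can reach 8.

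One qualification applies to RT Cycle 2. The hold of up to 2 days at Day 1 happens after bosentan has started, so what causes it may have arisen on bosentan itself.

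**Step 3. Expected numbers of patients.** Inputs from the documents: eight patients allocated 1:1, taken as 4 per sequence. Assumptions, because the documents give no values:
- pT: chance that a BOS+LRB cycle leads to a modification of the next cycle
- pR: the same chance after an LRB-alone cycle
- q: share of patients taking Cycle 3
- cycles are independent, everyone reaches Cycle 2, and a patient counts once per column

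Counted by modified cycle:
- BOS+LRB = 4·pR
- LRB alone = 4·[1 − (1 − pT)(1 − q·pR)] + 4·q·pT

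Counted by causing cycle:
- BOS+LRB = 4·pT·(1 + q)
- LRB alone = 4·pR·(1 + q)

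Worked case with pT = pR = 0.30 and q = 1. By modified cycle, BOS+LRB = 4 × 0.30 = 1.2 and LRB alone = 4 × (1 − 0.7 × 0.7) + 4 × 0.30 = 2.04 + 1.2 = 3.24. By causing cycle, both are 4 × 0.30 × 2 = 2.4.

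Each cell shows BOS+LRB vs LRB alone:

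| pT | pR | q | By modified cycle | By causing cycle |
|---|---|---|---|---|
| 0.30 | 0.30 | 0 | 1.2 vs 1.2 | 1.2 vs 1.2 |
| 0.30 | 0.30 | 0.5 | 1.2 vs 2.22 | 1.8 vs 1.8 |
| 0.30 | 0.30 | 1 | 1.2 vs 3.24 | 2.4 vs 2.4 |
| 0.15 | 0.30 | 0 | 1.2 vs 0.6 | 0.6 vs 1.2 |
| 0.15 | 0.30 | 0.5 | 1.2 vs 1.41 | 0.9 vs 1.8 |
| 0.15 | 0.30 | 1 | 1.2 vs 2.22 | 1.2 vs 2.4 |
| 0.30 | 0.15 | 0 | 0.6 vs 1.2 | 1.2 vs 0.6 |
| 0.30 | 0.15 | 0.5 | 0.6 vs 2.01 | 1.8 vs 0.9 |
| 0.30 | 0.15 | 1 | 0.6 vs 2.82 | 2.4 vs 1.2 |
| 0.10 | 0.40 | 0 | 1.6 vs 0.4 | 0.4 vs 1.6 |
| 0.10 | 0.40 | 0.5 | 1.6 vs 1.32 | 0.6 vs 2.4 |
| 0.10 | 0.40 | 1 | 1.6 vs 2.24 | 0.8 vs 3.2 |

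**Step 4. What the table shows.**
- With no Cycle 3, the columns are swapped exactly.
- With Cycle 3 and equal rates, LRB alone shows a false excess.
- If BOS+LRB causes more modifications, the direction is wrong at each uptake shown.
- If BOS+LRB causes fewer, the direction is wrong at low uptake and right at high uptake. At 0.10 and 0.40, the LRB-alone count is 0.4 + 1.84·q and equals 1.6 at q = 1.2 / 1.84 ≈ 0.65.

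**The case against.** The strongest objection is that the SAP never says a modification belongs to the modified cycle. Table 11.2.1.1 is an AE summary, and its rows speak of modifications associated with AEs. SAP 7.4 is about treatment administration, and the exclusion of Cycle 1 is a footnote to the exposure tables. A programmer could work from the AE record instead, since Listing 13.29 holds the action taken and Listing 13.16 links a modification to a reason and an adverse event. That would give attribution by cause. A delay could also be read as falling at the end of the earlier treatment. This stands: counting by modified cycle is inferred. But SAP 7.4 is the only place that defines how delays and reductions are derived, and the footnote points the same way. Two programmers could fill these rows differently and both claim to follow the plan.

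A second objection is that the information is already visible. Listings 11.1.2.3 and 11.1.3.2 give sequence, cycle and reason, from which the preceding treatment follows, and SAP 7.4 drops the delay and reduction tables in favour of listings when counts are very low. This also stands in part. A careful reader can reconstruct the cause, but the summary rows would still say something else.

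Third, the reach is small. These are four descriptive rows, and the planned model-based safety comparison (Table 11.5.1.1) has no delay or reduction row. This stands in full.

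**Conclusion.** The point holds within limits. On the natural reading of the footnote with SAP 7.4, modifications at TR Cycle 2, RT Cycle 2 and RT Cycle 3 would normally be credited to the treatment that did not cause them. TR Cycle 3 is attributed correctly, and a short RT hold at Cycle 2 may arise on bosentan.

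A reader might infer that the bosentan comparison for delays and reductions is simply reversed. The documents do not support that. The counting rule is inferred rather than stated, and the exact swap applies to Cycle 2 only. With Cycle 3 included, the bias depends on uptake, which the documents do not give. At the assumed 10% and 40% rates the direction is reversed below about 65% uptake and not above it. At equal rates there is no true difference to reverse, only a false one.

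The sizes rest on the assumed rates, independence between cycles and exactly four patients per sequence; replacements would add to the safety population. The mapping in Step 2 does not depend on the rates.

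AE, SAE and laboratory displays are untouched. So are Tables 11.1.2.1 and 11.1.3.1, which are by sequence and contain no attribution error. The rows belong to a named secondary safety endpoint, so the rule should be settled before the tables are produced.

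**What to change.** In the Table 11.2.1.1 footnote and in SAP 7.4:

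- Assign each delay or reduction to the treatment of the cycle in which the triggering AE or laboratory abnormality began. For the RT hold at Cycle 2 Day 1, the onset date decides.
- Use as denominator the patients who started, or were due to start, a cycle after that treatment.
- State how Cycle 3 is handled: whether its modifications enter the table, and whether a reduced dose carried forward from Cycle 2 counts again, since Protocol 7.5 does not allow re-escalation.

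A causing-treatment column in Listings 11.1.2.3 and 11.1.3.2 is optional. Tables 11.1.2.1 and 11.1.3.1 need no change.

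The cost is one derived variable and a few lines of SAP text. The reason and linked adverse event are already in Listing 13.16 and onset dates in Listing 13.29. Protocol 8.5.1 requires a laboratory abnormality that changes dosing to be recorded as an AE, so such triggers are covered. No new data are collected and no clinical rule changes.

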11.3 Serious Adverse Events and Deaths

11.3.1 Serious Adverse Events

Serious adverse events tables will be listed by total and sequence or differentiating by treatment (Test, Reference or both).

Type of toxicity and worst grade or severity by cycle and by patient will be summarized according to System Organ Class (SOC) and Preferred Term (PT) as per the MedDRA dictionary. Subsequent grouping of similar or clinically related items might be appropriate at the time of the analysis.

Tables will be organized by category of events using SOC and PT. Grades could be presented by separate or any other grouping at the time of the analysis.

If the number of SAEs are very low, these tables will not be presented and only listings will be shown.

Table 11.3.1.1 Treatment Related[†] (or with unknown relationship) SAEs. Worst grade per treatment

SOC/PT	BOS+LRB						LRB alone					
	All grades		Gr ≥ 3		Gr ≥ 4		All grades		Gr ≥ 3		Gr ≥ 4	
	N	%	N	%	N	%	N	%	N	%	N	%
...												

Notes: Percentage is based on number of patients by treatment, when applicable.

[†] Related to both or lorbinecetin or bosentan or with unknown relationship

BOS, bosentan; LRB, lorbinecetin.

Table 11.3.1.2 Lorbinecetin related[†] SAEs. Worst grade per treatment

SOC/PT	BOS+LRB						LRB alone					
	All grades		Gr ≥ 3		Gr ≥ 4		All grades		Gr ≥ 3		Gr ≥ 4	
	N	%	N	%	N	%	N	%	N	%	N	%
...												

Notes: Percentage is based on number of patients by treatment, when applicable.

[†] Related to lorbinecetin or with unknown relationship

BOS, bosentan; LRB, lorbinecetin.

Table 11.3.1.3 Bosentan related[†] SAEs. Worst grade per treatment

SOC/PT	BOS+LRB					
	All grades		Gr ≥ 3		Gr ≥ 4	
	N	%	N	%	N	%
...						

Notes: Percentage is based on number of patients by treatment, when applicable.

[†] Related to bosentan or with unknown relationship

BOS, bosentan; LRB, lorbinecetin.

Table 11.3.1.4 Treatment Related[†] (or with unknown relationship) SAEs. Worst grade per patient

SOC/PT	S1 (TR)				S2 (RT)				Total			
	All grades		Gr ≥ 3		All grades		Gr ≥ 3		All grades		Gr ≥ 3	
	N	%	N	%	N	%	N	%	N	%	N	%
...												

Notes: Percentage is based on number of patients in total and by sequence, when applicable.

[†] Related to both or lorbinecetin or bosentan or with unknown relationship

S1, Sequence 1; S2, Sequence 2; TR, test-reference; RT, reference-test.

Table 11.3.1.5 SAEs regardless of relationship. Worst grade per treatment

SOC/PT	BOS+LRB						LRB alone					
	All grades		Gr ≥ 3		Gr ≥ 4		All grades		Gr ≥ 3		Gr ≥ 4	
	N	%	N	%	N	%	N	%	N	%	N	%
...												

Notes: Percentage is based on number of patients by treatment, when applicable.
BOS, bosentan; LRB, lorbinecetin..

Table 11.3.1.6 SAEs regardless of relationship. Worst grade per patient

SOC/PT	S1 (TR)						S2 (RT)						Total					
	All		Gr ≥ 3		Gr ≥ 4		All		Gr ≥ 3		Gr ≥ 4		All		Gr ≥ 3		Gr ≥ 4	
	grades	N	%	N	%	N	%	N	%	N	%	N	%	N	%	N	%	
...																		

Notes: Percentage is based on number of patients in total and by sequence, when applicable.
S1, Sequence 1; S2, Sequence 2; TR, test-reference; RT, reference-test.

Listing 11.3.1.7 All SAEs[†]

Sequence	Treatment	Cycle	Subject	SOC	PT	Grade	AE	AE	AE	Start	End date
						status	Relationship	consequences			
group*											

[†]SAE narratives will be provided by the pharmacovigilance department

*BOS+LRB/LRB alone

11.3.2 Deaths

Table 11.3.2.1 Cause of death

	S1 (TR)		S2 (RT)		Total	
	N	%	N	%	N	%
Malignant disease						
Adverse Event(s)						
Other [‡]						
Total						

Notes: Percentage is based on number of patients who died by total and sequence, when applicable.

[‡]Specify

S1, Sequence 1; S2, Sequence 2; TR, test-reference; RT, reference-test.

Listing 11.3.2.2 Deaths

Sequence	Subject	Death date	Cause of death	No. of cycles administered	Time on treatment [†]	Time from last dose [‡] (days)

[†]Time on treatment is defined as the last administration date of lorbinecetin plus 31 days, death or the start date of the new therapy, whichever comes first, minus the first administration date.

[‡]Time from last dose defined as date of death minus date of last infusion.

11.4 Clinical Laboratory Evaluation

11.4.1 Hematological Abnormalities

Table 11.4.1.1 Hematological abnormalities: Worst grade per treatment

	BOS+LRB						LRB alone					
	All grades		Gr \geq 3		Gr \geq 4		All grades		Gr \geq 3		Gr \geq 4	
	N	%	N	%	N	%	N	%	N	%	N	%
Anemia												
Leukopenia												
Lymphopenia												
Neutropenia												
Thrombocytopenia												

Notes: Percentage is based on number of patients by treatment, when applicable.

BOS, bosentan; LRB, lirbinezidin.

Listing 11.4.1.2 Hematological abnormalities grade \geq 3

Treatment group [†]	Subject	Event	Grade

[†]BOS+LRB/LRB alone

Listing 11.4.1.3 Hematological tests not assessed by patient

Treatment group [†]	Subject	Lab. test

[†]BOS+LRB/LRB alone

Table 11.4.1.4 Hematological abnormalities: Worst grade per patient

	S1 (TR)			S2 (RT)			Total					
	All grades		Gr \geq 3	Gr \geq 4	All grades		Gr \geq 3	Gr \geq 4	All grades		Gr \geq 3	Gr \geq 4
	N	%	N	%	N	%	N	%	N	%	N	%
Anemia												
Leukopenia												
Lymphopenia												
Neutropenia												
Thrombocytopenia												

Notes: Percentage is based on number of patients in total and by sequence, when applicable.

S1, Sequence 1; S2, Sequence 2; TR, test-reference; RT, reference-test.

Listing 11.4.1.5 Hematological abnormalities by cycle grade \geq 3

Sequence	Subject	Event	Cycle	Grade

Listing 11.4.1.6 Hematological tests not assessed by cycle

Sequence	Subject	Cycle	Lab. test

